Low-Cost Platelet- Rich Plasma for Hemearthropathy

NCT06543368

May 2, 2024

STUDY PROTOCOL

Objectives

Hemophilic arthropathy, or hemarthropathy, results from recurrent accumulation of blood in the joints, leading to chronic pain, inflammation, and progressive joint damage. Effective nonsurgical treatment options for patients with hemophilic arthropathy are needed, but further research must be conducted to identify if safe conservative options, such as platelet-rich plasma (PRP) injections, can contribute to functional improvements and pain relief for this clinical population.

The objective of this study is to assess the feasibility of utilizing low-cost platelet-rich plasma (LC-PRP) preparation technique within the context of utilizing PRP for the treatment of hemophilic arthropathy. Specifically, this study aims to demonstrate the safety of this technique/treatment (no serious adverse events), evaluate LC-PRP composition (i.e., to assess if the prepared LC-PRP has similar cellular composition to reported values from commercially available PRP kits), and to measure patient improvement (e.g., pain, function, and satisfaction) following LC-PRP injection.

More specifically, this study will be guided by the following aims:

Aim 1: Prospectively evaluate clinical outcomes in a cohort of patients with bleeding disorders for pain and functional measures over six months. Hypothesis: Subjects who receive LC-PRP will demonstrate improvements in pain and function at three months, specifically on the WOMAC score (knee), American Orthopaedic Foot and Ankle Society (AOFAS) Ankle-Hindfoot score (ankle), and the Quick Disabilities of Arm Shoulder and Hand (QuickDASH) score (elbow).

Aim 2: Evaluate the total cost of the procedure, including the cost of supplies, staff time, and pharmaceutical components. Hypothesis: The total cost of the procedure will be comparable to the standard-of-care injection, corticosteroid.

Aim 3: Evaluate the likelihood of adverse events related to the procedure, namely repeat bleeding into the joint or infection following the procedure. Hypothesis: Subjects who receive a LC-PRP injection will not have an increased risk of adverse events compared to the standard-of-care injection, corticosteroid.

METHODS

Study Design

This single-arm, prospective cohort pilot study is designed to evaluate the feasibility of using LC-PRP to treat pain and dysfunction from hemarthropathy. Consecutive patients eligible for a standard-of-care injection will be enrolled from the Utah Center for Bleeding and Clotting Disorders. A total of 20 joints (estimated 10-15 patients) will receive PRP injections, performed at day 0 and 3 weeks, for a total of two injections – two injections have demonstrated superior outcomes to one,¹ and will increase our number of injections to improve the proof of feasibility.

Sample

Adult patients with symptomatic hemarthropathy of the ankle, knee, or elbow, based on radiographs within the last 24 months will be eligible for inclusion. Patients must have failed at least six weeks of conventional conservative treatments (e.g., medication or physical therapy). Exclusion criteria will include recent (last two years) surgery to the affected joint, prior joint replacement, prior orthobiologic injection into the affected joint, thrombocytopenia, inability to receive factor prior to PRP injection, active systemic or local infection at the site of injection, non-ambulatory patients, body mass index (BMI) over 50, and recent (six month) or current corticosteroid injection/intake. Patients with hemarthropathy in multiple joints will be eligible for up to 2 joints if multiple fit the criteria.

LC-PRP Preparation

The full methodology is presented in the Appendix. To summarize, 45mL of blood will be collected and processed to result in 3-9 mL of neutrophil-poor PRP, depending on the joint injected (i.e., 3 mL for ankles/elbows, 9 mL for knees). Whole blood will be collected into three 20 mL syringes containing ACD-A anticoagulant. No platelet activators will be used in this process. The flange and the plunger of the syringes will be clipped off with shears and placed into a centrifuge with counterbalance. The centrifuge will run at 750 G for

five minutes. The three syringes will then be removed, and each will be consecutively attached to a 3-way stopcock. For each syringe, the platelet-poor (upper) portion of the plasma will be directed to a waste syringe, then the remaining platelet-rich (lower) portion of the plasma will be directed to a syringe containing the final PRP. This process will be repeated for the 3 syringes. No more than 5 minutes will elapse between stages of the procedure. No more than 30 minutes will elapse between completion of PRP preparation and injection; during that time, the PRP will be placed on a rocker to avoid layer separation. Blood will not be exposed to air at any point during this process, and all connections between syringes will be accomplished via Luer-Lok. PRP preparation/processing time will be monitored.

LC-PRP Injection

Peri-procedure factor management (if applicable) will be directed by the participant's primary hematologist. Injections are to be performed on day 0 and at 3 weeks, for a total of two injections per joint. This process will involve an ultrasound-guided intra-articular knee, ankle, or elbow injection by an experienced sports medicine provider (PI [name]) with a 23 g needle after local anesthesia with 1% lidocaine to the extra-articular structures, namely the skin and joint capsule, to increase comfort.

Blood Analysis: LC-PRP Composition

All subjects will have less than 1mL of their whole blood and prepared PRP analyzed, with a complete blood count (CBC) with differential for each injection. Importantly, we will include all data required in the PRP minimum reporting standards,² including “platelet, differential leukocyte, and red cell analysis of all samples.”

Questionnaires

We will collect demographic information along with baseline and follow-up (i.e., 1 month, 3 months, and 6 months following second injection) patient reported outcomes, namely the WOMAC (knee), FAOS (ankle), and the QuickDASH (elbow). Surveys will be administered, and data will be stored, in REDCap.³⁻⁵ Additionally, patient surveys will assess any adverse events, pain, global satisfaction, global injection satisfaction, and medications. At 3 and 6 weeks, we will inquire about adverse events related to the procedure, monitoring closely for any reported joint bleeds or infections following PRP injections.

DATA ANALYSIS

Statistical Analysis Plan

Whole blood and LC-PRP outcomes (e.g., platelet concentration, platelet count) will be summarized with descriptive statistics (i.e., mean and standard deviation). Patient reported outcome measures (e.g., global assessment, EQ-5D, WOMAC [including total score and pain, stiffness, and function subscores], QuickDASH, FAOS) will be described via median and interquartile range (IQR) at baseline and follow-up (i.e., 1, 3, and 6-months). Frequencies and percentages will be used to summarize patient satisfaction with the study joint (at baseline and all follow-up points) and adverse events. As this is a feasibility study and therefore is not intentionally powered for clinical outcomes, no statistical hypothesis testing will be performed. See example tables 1 through 6 below for further details pertaining to planned analyses and study reporting.

Example Table 1: Demographics

| | n | % | Mean | SD |
|---|---|---|------|----|
| Total patients | | | | |
| Joints | | | | |
| Elbows | | | | |
| Knees | | | | |
| Ankles | | | | |
| Age | | | | |
| Body mass index (kg/m²) | | | | |
| Duration of symptoms (y) | | | | |
| Sex | | | | |
| Female | | | | |
| Male | | | | |
| Hemophilia type | | | | |

| | | | |
|---|--|--|--|
| Hemophilia type A | | | |
| Hemophilia type B | | | |
| Hemophilia severity | | | |
| Mild | | | |
| Moderate | | | |
| Severe | | | |
| Baseline satisfaction with joint | | | |
| Very unsatisfied | | | |
| Unsatisfied | | | |
| Neither satisfied nor unsatisfied | | | |
| Satisfied | | | |
| Very satisfied | | | |

Example Table 2: Whole blood and PRP cellular composition

| | Whole blood | | PRP | |
|--|-------------|----|------|----|
| | Mean | SD | Mean | SD |
| Volume | | | | |
| Platelet concentration, 10 ³ per uL | | | | |
| Platelet count (billion) | | | | |
| Platelet extraction (%) | | | | |
| Concentration factor | | | | |
| WBC concentration, 10 ³ per uL | | | | |
| - Neutrophils | | | | |
| - Lymphocytes | | | | |
| RBC concentration, 10 ⁶ per uL | | | | |
| Hb concentration, g/dL | | | | |

Example Table 5. Satisfaction with study joint at baseline and and follow-up

| | Baseline | 1 Month | 3 Months | 6 Months |
|-----------------------------------|----------|---------|----------|----------|
| Satisfaction with Joint | | | | |
| Very unsatisfied | | | | |
| Unsatisfied | | | | |
| Neither satisfied nor unsatisfied | | | | |
| Satisfied | | | | |
| Very satisfied | | | | |

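### A single-arm pilot with no corticosteroid reference cannot demonstrate safety or support the Aim 3 hypothesis of no increased risk; both statements should become estimation aims

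*Combined protocol and SAP*

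**What the plan says.** The Objectives section says the study aims to "demonstrate the safety of this technique/treatment (no serious adverse events"). Aim 3 opens in descriptive terms, "Evaluate the likelihood of adverse events related to the procedure, namely repeat bleeding into the joint or infection following the procedure", and then adds a comparative hypothesis: "Subjects who receive a LC-PRP injection will not have an increased risk of adverse events compared to the standard-of-care injection, corticosteroid".

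Under Study Design, "This single-arm, prospective cohort pilot study is designed to evaluate the feasibility", and "A total of 20 joints (estimated 10-15 patients) will receive PRP injections". Under Sample, "Patients with hemarthropathy in multiple joints will be eligible for up to 2 joints if multiple fit the criteria". The LC-PRP Injection section gives each joint two injections.

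The Statistical Analysis Plan summarises adverse events by frequency and percentage. It says that, as a feasibility study not powered for clinical outcomes, the trial will do no hypothesis testing. Example Table 6 lists adverse events in one n (%) column, with no comparator column and no indication whether the percentage is of patients, joints or injections. No corticosteroid event rate, source for one, or margin appears in the document.

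**The concern.** Two sentences in the Objectives commit the study to conclusions that its design and analysis cannot produce. The first treats the absence of serious events as a demonstration of safety. The second asserts a comparison for which the plan has no second quantity.

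If the study runs exactly as written and no serious event occurs, the protocol's own words would license a report that safety was demonstrated and that risk was no higher than with corticosteroid. The first conclusion would rest on 10-15 patients and the second on no comparative data. The missing denominator adds to this, because the same count can be printed as percentages that differ fourfold.

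**Working it through.** **The plan's own figure.** The document gives no event rate, error level, power or precision target, so the 20 joints can be neither reproduced nor called wrong. The arithmetic is consistent: 20 joints / at most 2 per patient = at least 10 patients, which fits 10-15; 20 joints × 2 injections = 40 injections; one patient can contribute 2 × 2 = 4 injections.

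**Aim 3 hypothesis.** A statement of no increased risk needs a risk under LC-PRP, a risk under corticosteroid, and a rule for what counts as no increase. The plan supplies data for the first only. More patients would not change that, and the conclusion needs no assumed rate.

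**Safety objective.** With zero events in n independent units, the exact upper 95% limit is 1 − 0.025^(1/n) two-sided and 1 − 0.05^(1/n) one-sided.

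| Unit | n | Two-sided | One-sided |
|---|---|---|---|
| Patients, low estimate | 10 | 30.8% | 25.9% |
| Patients, high estimate | 15 | 21.8% | 18.1% |
| Joints, taken as independent | 20 | 16.8% | 13.9% |
| Injections, taken as independent | 40 | 8.8% | 7.2% |

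The last two rows are optimistic, because joints and injections in the same patient are not independent. They also describe a different quantity, the risk per joint or per injection. Suppose 10 patients each have two joints. Even with full independence, a one-sided limit of 7.2% per injection over four injections is 1 − (0.05^(1/40))^4 = 1 − 0.05^(1/10) = 25.9% per patient, the same as in the first row. The smaller unit adds no assurance for the patient.

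**Event-free patients needed.** To exclude a true risk t, n must be at least ln(0.025)/ln(1 − t) two-sided, or ln(0.05)/ln(1 − t) one-sided. For t = 10% this gives 36 or 29 patients; for t = 5%, 72 or 59. All exceed 15.

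**How easily the criterion is met.** The document gives no serious-event rate, so these risks are assumptions. The probability of no event is (1 − p)^n:

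| Assumed per-patient risk p | n = 10 | n = 15 |
|---|---|---|
| 1% | 90% | 86% |
| 2% | 82% | 74% |
| 5% | 60% | 46% |
| 10% | 35% | 21% |

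**Denominator.** One event is 1/10 = 10.0% or 1/15 = 6.7% of patients, 1/20 = 5.0% of joints, or 1/40 = 2.5% of injections.

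**The case against.** The strongest reply is that the document already presents itself as a pilot. Safety sits under a feasibility objective, the bracketed gloss is something that can simply be observed, Aim 3 opens with a descriptive verb, and the Statistical Analysis Plan rules out hypothesis testing. No decision rule depends on the safety result. Much of this stands: descriptive reporting is appropriate, and Aim 3's opening sentence needs no defence. But the testing disclaimer speaks of power for clinical outcomes and withdraws neither the aim to demonstrate safety nor the comparative hypothesis.

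A second reply is that 40 injections give tighter limits than 10-15 patients. That is true only per injection and under independence.

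Four stronger readings are tempting but not supported:

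- A reader might infer that the design or the 20 joints is at fault. With no stated rate or precision target, the documents give no basis for that.
- A reader might blame the lack of a corticosteroid rate on the exclusion for "recent (six month) or current corticosteroid injection/intake". The single-arm design is the reason; that exclusion would not by itself prevent a concurrent corticosteroid group.
- A reader might infer that the zero-event criterion would probably be met even if LC-PRP doubled the corticosteroid risk. That criterion applies to serious events, whereas Aim 3 concerns bleeds and infection, for which no zero-event rule is stated. The result would also depend entirely on assumed rates.
- A reader might infer from Example Table 6 that infections go unrecorded. The Questionnaires section plans to ask about joint bleeds and infections, and the table is an example with an open category for other events.

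**Conclusion.** The concern holds as a mismatch between two statements in the Objectives and an otherwise acceptable descriptive pilot. The Aim 3 hypothesis cannot be assessed at any sample size, because no comparator or reference rate exists; this rests on the document alone. The safety claim fails on precision. Zero serious events among 10-15 patients leaves per-patient risks of up to 30.8% or 21.8% (two-sided), or 25.9% or 18.1% (one-sided), unexcluded. Those limits assume that patients are independent and that every injected patient's adverse-event status is known; incomplete follow-up would widen them. The correction is worth making because it changes what the study may conclude, but it does not touch enrolment or conduct.

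**What to change.** Restate the safety objective and Aim 3 as estimating the proportion of injected patients with a joint bleed, infection or serious adverse event, with exact two-sided 95% confidence intervals. Report each event type separately.

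State in the Statistical Analysis Plan and Example Table 6 that the denominator is patients injected and the numerator is patients with at least one such event. Show joint and injection counts alongside, without intervals that treat them as independent.

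Delete *demonstrate* for safety, and delete the no-increased-risk hypothesis. If a corticosteroid comparison is wanted, name an external rate and its source, and present it as descriptive context with no conclusion about relative risk.

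Separate rows for infection and serious events in Example Table 6 would follow naturally from the restated aim, but they are optional layout.

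The cost is the wording of one objective and one aim, a stated denominator and a few exact intervals. No patients or visits are added. The downside is a more modest safety claim, which is what these data can support.

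### Aim 1 hypothesises improvement at three months, but the SAP prose summarises scores visit by visit and names no within-joint change from baseline (example Tables 3 and 4, not visible here, may do so)

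*Combined protocol and SAP*

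**What the plan says.** Aim 1 (Objectives) states the hypothesis: "Subjects who receive LC-PRP will demonstrate improvements in pain and function at three months". It names the WOMAC for the knee, the QuickDASH for the elbow and, for the ankle, the "American Orthopaedic Foot and Ankle Society (AOFAS) Ankle-Hindfoot score (ankle").

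The Questionnaires section collects these outcomes at baseline and at three follow-up times, "namely the WOMAC (knee), FAOS (ankle), and the QuickDASH (elbow"). It adds that "patient surveys will assess any adverse events, pain, global satisfaction, global injection satisfaction, and medications".

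The Statistical Analysis Plan says that patient-reported outcomes "will be described via median and interquartile range (IQR) at baseline and follow-up (i.e., 1, 3, and 6-months"). It rules out hypothesis testing because the study is a feasibility study not powered for clinical outcomes. It then refers onward: "See example tables 1 through 6 below for further details pertaining to planned analyses and study reporting". In the supplied text Tables 1, 2, 5 and 6 can be read; Tables 3 and 4 cannot. Table 5 (satisfaction with the joint) has one column per visit and no change column.

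Study Design sets 20 joints in an estimated 10 to 15 patients.

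**The concern.** Improvement is a change from a joint's own starting point. The prose names a median and IQR at each visit, and a set of such summaries does not determine how much individual joints changed or how many improved. If the prose were all that was reported, a reader would judge Aim 1 from the difference between two group medians.

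Two things could then go wrong. The difference in medians need not equal the median change, and it says nothing about how change is spread over joints. And if some joints have no follow-up score, the two medians rest on different joints, so the difference can move although no joint has changed. The 20 joints are divided among three instruments, so each median rests on few values and one or two missing joints count. With no test planned, the descriptive summary is the only evidence on Aim 1.

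**Working it through.** The plan states no figure on this point (no effect size, power or derivation of the 20 joints), so there is nothing to reproduce. The check is a reading of the text followed by an illustration.

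**Text.** No readable part of the document names a change from baseline, a paired difference or a count of joints improved for the patient-reported scores. The scores needed to compute change are planned at baseline and at each follow-up.

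**Assumptions.** The documents give no joint split, scores, SD, correlation or missingness. An even split gives 20 / 3 = 6.7, so 7 joints per instrument are assumed, with a lower score better. Baseline scores are 20, 30, ..., 80 (median 50, IQR 35 to 65). Follow-up scores are 10, 20, ..., 70 (median 40, IQR 25 to 55). The difference in visit medians is 40 − 50 = −10.

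**1. Pairing.** The 7! = 5,040 ways of matching follow-up to baseline scores all share these visit summaries. The median within-joint change is:

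| Correlation | Pairings | Change −10 | Change 0 | Change −20 |
|---|---|---|---|---|
| ≥ 0.5 | 672 | 500 (74%) | 86 (13%) | 86 (13%) |
| ≥ 0.7 | 222 | 186 (84%) | 18 (8%) | 18 (8%) |
| ≥ 0.9 | 17 | 17 (100%) | 0 | 0 |

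At correlation ≥ 0.5, 4 or 5 of the 7 joints improve in (286 + 246) / 672 = 79% of pairings. The extremes are 2 joints (7 pairings) and 7 joints (1 pairing).

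One case at correlation 0.82 has changes 0, 0, −30, 0, −20, 0, −20. The median change is 0, with 3 joints better, 4 unchanged and none worse, yet the visit medians fall by 10.

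**2. Missing joints.** Suppose every joint stays at its baseline score and 2 of the 7 are missing at follow-up, which gives 21 possible pairs.
- One missing below 50 and one above: 3 × 3 = 9 pairs, difference in visit medians 0.
- Both below 50, or 50 itself and one below: 3 + 3 = 6 pairs, difference +10.
- The mirror image: 6 pairs, difference −10.

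The paired change is 0 in all 21. With 1 missing, the difference is 0 in 1 case, +5 in 3 and −5 in 3.

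**3. Precision.** Simulation with bivariate normal scores, SD 20, true change −10, n = 7 and 200,000 replicates. The ratio is (SD of difference in medians / SD of median paired change)².

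| Correlation | SD, difference in medians | SD, median paired change | Variance ratio |
|---|---|---|---|
| 0.3 | 11.53 | 10.83 | 1.13 |
| 0.5 | 10.44 | 9.19 | 1.29 |
| 0.7 | 8.92 | 7.09 | 1.58 |
| 0.8 | 7.83 | 5.80 | 1.82 |

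At n = 5 the ratios are 1.12, 1.26, 1.51 and 1.71; at n = 10 they are 1.12, 1.24, 1.47 and 1.66.

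**The case against.** The strongest reply is that the answer may lie in tables that cannot be read here. Among the readable tables, none covers the WOMAC, QuickDASH, FAOS or EQ-5D scores, so Tables 3 and 4 probably do. If they have a change column, what remains is to align the prose. This stands in full. A reader might infer from the visit-only layout of Table 5 that the trial plans no change analysis at all. The documents do not support that: Table 5 concerns ordinal satisfaction and says nothing about the layout of Tables 3 and 4.

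The second reply is that visit medians suit a descriptive feasibility pilot. That also largely stands. The hypothesis sets no amount or proportion, so a fall in the group median is a fair group-level description, and no decision rule or sample size depends on it. In the simulation at correlation 0.5, the difference in medians has the right sign in 83% of replicates and the median paired change in 86%; at 0.8 the figures are 90% and 96%. The loss is small.

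The third reply is that every input to the illustration is assumed, and that its discrepancies are symmetric (86 pairings each way), so it shows no systematic bias. This is correct. The missing-joint example also assumes no measurement noise, which makes the paired change 0 by construction.

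What survives is narrower: the paired summary describes the hypothesised quantity directly, needs no new data and does not conflict with the no-testing rule.

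**Conclusion.** The point holds at low severity, as a nearly free improvement, and only for the SAP prose. Aim 1 is about improvement at three months, while the prose names only visit-wise medians and IQRs. It falls away, or shrinks to a wording change, if Tables 3 and 4 already show within-joint change.

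The illustration shows that the two summaries can differ, not that they will. They agree in about three quarters of pairings at correlation 0.5 or more and always at 0.9 or more. The variance penalty of about 1.1 to 1.8 applies for correlations 0.3 to 0.8. All of this rests on 7 joints per instrument and on assumed scores, SD, correlation and missingness.

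A reader might go further and conclude that the planned summaries would mislead or cannot address Aim 1. The documents do not support that: no figure in the plan is wrong, and no dropout rate is given from which to judge the missing-joint effect.

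**What to change.** First check example Tables 3 and 4. If they show change from baseline, add a sentence to the SAP prose saying so.

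Otherwise add, for the WOMAC, FAOS, QuickDASH and pain, a descriptive within-joint change from baseline at 1, 3 and 6 months, with 3 months as the key time point. For each, report:
- the number of joints with both values;
- the median and IQR of change;
- the numbers of joints better, unchanged and worse, with each instrument's direction of benefit stated;
- the number missing.

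Keep the visit medians as supporting information and add no test.

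For the ankle, Aim 1 names the AOFAS score, while the Questionnaires section and the SAP name the FAOS. Until these are reconciled, ankle change can be reported only on the FAOS.

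The cost is a few sentences and minor programming on scores already planned; the 20 joints and the no-testing rule are unaffected. Paired change does not remove bias from informative dropout, so the missing counts must stand beside it.
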